6. **Urinalysis** will be collected once at baseline and once at the end of randomized medication phase by the nurse or physician and sent to an off-site laboratory for examination. The test includes color, appearance, specific gravity, pH, protein, glucose, occult blood, ketones, leukocyte esterase, nitrite, bilirubin urobilinogen, and microscopic examination of urine sediment. Any abnormal results are brought to the attention of the principal investigator or study physician (Visits 1 and 40).
7. **Qualitative Benzoyllecgonine Screens (UBT)**: Qualitative urine benzoyllecgonine levels will be obtained at each study visit using One Step Drug Screen Test Cards (Cliawaived) or tested at the Main Toxicology Laboratory at the Philadelphia VA Medical Center.
8. **Qualitative Urine Drug Screens (UDS)**: Qualitative (emit) urine toxicology of benzodiazepines, barbiturates, amphetamines, and opiates will be done weekly during the baseline phase, the medication phase of the trial and once at the end of randomized

medication phase (Visits 1, 4, 7, 10, 13, 16, 19, 22, 25, 28, 31, 34, 37, 40) at the Main Toxicology Laboratory at the Philadelphia VA Medical Center.

9. **Urine Pregnancy Test** (UPT): A specimen will be collected once at baseline, every four weeks during the randomized medication phase, and once at the end of randomized medication. Samples will be tested at the Main Toxicology Laboratory of the Philadelphia VA Medical Center (Visits 1, 19, 40).

Screening: Subject will have three screening visits. The visits must be completed within a minimum of one week and a maximum of four weeks. The screening period is referred to as "Week 1".

Regular Evaluation Visits: Subjects will be in contact with the research staff three times weekly throughout the medication Phase of the study (weeks 2-13), preferably every Monday, Wednesday, and Friday (M,W,F). A few basic measures will be taken at each visit, UDS for BE, breathalyzer, TLFB, and adverse event recording. At the first evaluation visit each week, the following additional measures will be accomplished by research staff: Urine drug screen for benzodiazepines, barbiturates, opiates, marijuana, methadone, amphetamine, CSSA, Subject (CGIS), Treatment Services Review (TSR), Minnesota Cocaine Craving Scale (MCCS), and Cocaine Craving Questionnaire (CCQ). This will take about 45 minutes. At the first visit of week 7 and week 13, research staff will administer the Addiction Severity Index (ASI) (about 20 minutes) and obtain the Treatment Group prediction Form. Each subject will meet weekly with a nurse or physician for MM sessions to assess clinical status, monitor vital signs and weight, dispense study medications, pill count, monitor concomitant medications, monitor adverse events and provide Clinical Global Impressions (CGI) ratings. This will take about 15-30 minutes. The nurse or physician will also complete a Treatment Group Prediction Form at week 7 and visit 40.

The subject's individual therapist will complete the CGI weekly weeks 2-13 and complete the Treatment Group Prediction Form at week 7 and visit 40(about 3 minutes).

End of Medication Phase Evaluations: These will be done after the completion of Week 13, or at the completion of the trial in participants who are discontinued from the trial prematurely.

At this time, a nurse or physician will conduct the following procedures: vital signs and weight, physical exam, electrocardiogram, concomitant medications, adverse events, obtain blood samples for chemistry including liver function tests and CO2, CBC, obtain a urinalysis, CGI, pill count, and Treatment Group Prediction Form.

Research staff will conduct the following procedures: breathalyzer, CO, cotinine, ASI, TSR, CSSA, CCQ, SCL-90-R, RAB, BSCS, CGI, MCCS, TLFB, UDS, UBT, UPT, and Treatment Group Prediction Form. A clinically trained diagnostician will conduct the Ham A and Ham D. This entire visit will take about 120 minutes.

Psychosocial Treatment: Subjects will receive weekly psychotherapy from week 2 through week 13. This results in 12 individual, cognitive behavioral therapy (CBT) sessions, each lasting 50 minutes, for each subject.

CBT is based on general principles of social learning theory, which assume that disordered individuals have coping skill deficits that prevent them from managing high-risk situations. CBT utilizes direct practice, role playing and fine-tuning of new coping skills to achieve treatment goals.

The CBT we will use is based on relapse prevention principles. We are currently using, as part of another study, Project MATCH's CBT manual that [name] has adapted for use in treating both cocaine and alcohol dependence (Kadden et al., 1992, Carroll et al., 1991, 1994). We will follow this manual in all procedures. We have had much experience with this manualized therapy as we have used it to treat over 300 cocaine and alcohol dependent subjects in two previous clinical trials.

CBT will be provided by a clinician who will receive training and day-to-day supervision from [name], the TRC's Clinical Director. All CBT visits will be audiotaped and a minimum of two treatment sessions (an early and later session) will be rated for clinician adherence to the respective treatment principles and therapeutic alliance. [name] is trained in CBT principles and is familiar with [name] manual. She will provide the adherence ratings for the audiotapes. We will use [name] adherence checklists, which are written based on general principles of CBT and can be used in both core and elective sessions. These tapes will also assist in the supervision provided to the clinician and reduce drift.

Subjects will also receive once weekly Medical Management (MM)—an intervention developed as part of NIAAA's COMBINE that provides advice and support from medical practitioners concomitantly with dispensing medications and checking safety and compliance. The main goal of the intervention is to increase medication compliance. All subjects will receive regularly scheduled manualized adherence enhancement therapy for cocaine dependence. The initial MM session is an hour; follow-up sessions last no more than 15-30 minutes.

After the initial MM visit, subjects will meet with their nurse for 15-30 minutes for a total of 12 visits, primarily to dispense varenicline and assess varenicline safety (adverse events), treatment adherence (pill counts and visit attendance), and drinking / cocaine use status. The content of each visit is fully outlined in the MM manual (see appendix) and is briefly outlined in the following tables.

Table 2. Medical Management (MM): Content of Initial Visit

- Review with participant their biopsychosocial status, using the Clinician Report from the MM manual.
- Discuss with participant the role of the MM clinician: Safety, Education, Support
- Educate participant about his/her cocaine disorder and about the medication, i.e., varenicline
- Record baseline safety information
- Discuss importance of medication adherence --develop a plan for medication adherence
- Encourage attendance at CBT therapy visits, MM visits and self-help support groups

Table 3. Medical Management (MM): Content of Follow-up Visits

- Brief check on medical functioning
- Determine participant status re: using cocaine? Medication taking?
- Give support and advice based on participant status

Nurse Recruitment and Training: The Nurse will be responsible for interacting clinically with the subjects. Training and supervision will focus on the clinical skills and pharmacological knowledge needed to manage individual cases within the parameters of MM. The training will also aim to impart a high level of personal responsibility for the welfare of study subjects.

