Protection of Subjects: Potential subjects will be screened for medical illnesses that would preclude the use of varenicline. Subjects selected for the study will be monitored closely. Subjects will be evaluated three times a week while receiving study medication. Adverse events will be monitored by research staff at weekly visits, and the psychiatrist or nurse will be available at other visits to assess the subject if needed. At the conclusion of medications, an end of study physical will be completed and the baseline laboratory tests, including EKG, will be repeated. Subjects will be given a 24 hour emergency number they can call if necessary. Adverse events: If the subject is discontinued in treatment due to a serious adverse event, the subject will be followed clinically by medical staff until the adverse experience resolves itself and becomes stable. Subjects taking concomitant medications will be monitored closely for signs of toxicity. Subjects with a history of current severe psychiatric symptoms, use of any investigational medication within the last 30 days, AIDS or other serious illness which may require hospitalization during the study, impaired renal function or known liver disease, will be excluded from the study. Pregnant women or women who refuse to use acceptable forms of birth control will be excluded from the study. Urine pregnancy tests will be performed monthly.

The dose of varenicline will be started at 0.5 mg BID and increased to 1.0 mg BID by the end of the first week of medication therapy.

Venipuncture will be carried out with good aseptic technique by a nurse or physician. Venipuncture sites will be monitored carefully for signs of infection.

If a subject experiences an adverse event, appropriate evaluation and management will be undertaken. This may include medical management, a reduction in study of medication, a temporary cessation of study drug, or early termination from the trial, if necessary.

Strict confidentiality will be maintained. Clinical records will be stored in a restricted location and only the research team and clinical staff assigned to the care of the individual subjects will have access to the records. An exception to this rule will be made for representatives of the FDA and the National Institute on Drug Abuse (NIDA) and contract monitors and or auditors. The subject will be informed of these exceptions in the informed consent document.

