5.2 Treatment Regimen

Study medication will be initiated in Week 2. The research physician or nurse will explain the dosing regimen and subjects will be randomized to receive either varenicline or placebo. The statistician will randomize subjects to either varenicline or placebo using a computer-generated program of urn randomization, based on specified criteria that are described below.

The dose of varenicline will begin at 0.5 mg daily, and will be titrated up to the target daily dose of 2.0 mg/day at the start of the second week of medication (see Table 1). If adverse events occur, the physician or nurse may keep the dose the same or reduce to fewer pills. If the side effects subside, subjects can be re-challenged or kept at a lower number of pills. During the last week of the medication phase of the trial, varenicline will be reduced to 1.0 mg daily.

Pharmacotherapy will be completed by the end of the 13th week. If tolerated, subjects will be taking the maximum daily dosage (2.0 mg of varenicline or identical appearing capsules) for 10 weeks (Weeks 3-12).

Table 1. Dosing Schedule (taken from package insert)

| Wk. | Daily Dose |
|--------------|---------------------------|
| 2 (days 1-3) | 0.5 mg |
| 2 (days 4-7) | 0.5 mg BID (1.0 mg daily) |
| 3 | 1.0 mg BID (2.0 mg daily) |
| 4 | 1.0 mg BID (2.0 mg daily) |
| 5 | 1.0 mg BID (2.0 mg daily) |
| 6 | 1.0 mg BID (2.0 mg daily) |
| 7 | 1.0 mg BID (2.0 mg daily) |
| 8 | 1.0 mg BID (2.0 mg daily) |
| 9 | 1.0 mg BID (2.0 mg daily) |
| 10 | 1.0 mg BID (2.0 mg daily) |
| 11 | 1.0 mg BID (2.0 mg daily) |
| 12 | 1.0 mg BID (2.0 mg daily) |
| 13 | 0.5 mg BID (1.0 mg daily) |

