There have been no severe interactions noted between varenicline and any other drugs. Nonetheless, in the proposed study, weekly monitoring by a nurse or physician provides a safety net. We will be monitoring adverse events via self-reports, BAC readings, and liver enzymes collected routinely during the trials. Side effects can be treated by lowering the dose of study medications or discontinuing the study medications when necessary. The subject will be discontinued from medications if he or she has experienced a medication associated serious adverse event (SAE), cannot tolerate minimum dosages of study medication, or becomes pregnant. Any subject who is discontinued from the study medications can still complete the CBT portion of the treatment. If the subject reports an SAE, the subject will be followed until the event is resolved. Federal, sponsor, and institutional guidelines are followed for reporting SAEs.

Clinical Deterioration and/or Suicide Risk Management: All of the investigators have had experience managing and referring subjects under these conditions. We follow the TRC's standing emergency policy when managing clinical deterioration related to addiction or psychiatric symptomatology for all of our subjects. At the weekly visit, subjects are evaluated for the presence or persistence of any symptoms indicative of clinical deterioration due to a rapidly increasing problem with cocaine use, drinking, and/or psychiatric symptoms, including suicidality. Between visits, subjects are instructed to contact their treating physician or an authorized research staff member in the event that disturbing symptoms become evident. In all cases, these subjects are immediately evaluated, and if deemed appropriate, are referred to clinical treatment. If possible, they will be maintained in the trial as long as all it is deemed safe to do so. Also, any additional treatment is recorded for data analysis purposes. At any time, subjects who are severely suicidal or at high risk of medical or physical harm will be immediately discontinued from the trial. All subjects who are discontinued from the trial are still encouraged to attend the end of treatment visit.

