6.1 Visit 1 (screening)

All screening procedures are to be completed prior to randomization (visits 1, 2, or 3). They may not necessarily be completed at the exact visit noted below.

Nurse or physician:

1. Informed consent and consent quiz
2. Medical history
3. Physical Exam (PE)
4. Vital signs weight (VITALS)
5. Electrocardiogram (EKG)
6. Concomitant medications (CONMEDS)
7. Adverse Events (AE)
8. CBC and blood chemistry including liver function tests (LFT) and CO2.
9. Urinalysis (UA)
10. Clinical Global Impression Scale, Observer (CGIO)
11. Supplemental questions
12. Clinical Institutes Withdrawal Scale for Alcohol Revised (CIWA AR)

Research staff

1. Breathalyzer (BAL)
2. CO
3. Cocaine Selective Severity Assessment (CSSA)
4. Treatment Services Review (TSR)
5. Minnesota Cocaine Craving Scale (MCCS)
6. Cocaine Craving Questionnaire (CCQ)
7. Fagerstrom Nicotine Tolerance Questionnaire (FNTQ)
8. Brief Substance Craving Scale (BSCS)
9. Multiple Choice Procedure (MCP)
10. Delay Discounting Questionnaire (DD)
11. Risk Assessment Battery (RAB)
12. Symptom Checklist-90-Revised (SCL-90-R)
13. Timeline Follow Back (TLFB)
14. Urine drug screen other than cocaine (UDS)
15. Urinary BE level (qualitative)
16. Cotinine
17. Clinical Global Impression Scale, Subject (CGIS)
18. Urine pregnancy test (UPT)(females)
19. Short Form Health Survey (SF-36)

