12. UBT
13. BAL
14. TLFB
15. AE
16. ASI at visit 19
17. Treatment Group Prediction Form visit 19
18. UPT at visit 19 (females)
19. Any earned fishbowl draws completed and voucher earnings delivered

6.5 Second visit of each study week during randomized medication phase: Visit 5, 8, 11, 14, 17, 20, 23, 26, 29, 32, 35, 38

CBT Therapist

1. CBT Psychotherapy

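### Urine pregnancy tests are promised every four weeks on medication, but the visit lists schedule only one between baseline and the end of dosing

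*Combined protocol and SAP*

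**What the plan says.** Two places promise testing about every four weeks. Section 1.3 (Protection of Subjects) says: "Urine pregnancy tests will be performed monthly". Section 6, Laboratory Measurements, item 9 says: "A specimen will be collected once at baseline, every four weeks during the randomized medication phase, and once at the end of randomized medication".

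The schedules give less. Item 9 closes by naming visits 1, 19 and 40. Section 6.1 lists the test at visit 1 and section 6.7 lists it at visit 40. In the medication phase the only entry is in section 6.4: "UPT at visit 19 (females".

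A stopping rule depends on the result. Under section 5.2, medication stops for a subject who "cannot tolerate minimum dosages of study medication, or becomes pregnant". The same section says when dosing ends: "Pharmacotherapy will be completed by the end of the 13th week". Section 6 places the end-of-medication evaluation, visit 40, after week 13.

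**The concern.** The narrative and the visit lists cannot both be followed, and study staff usually work from the visit lists. If they do, women who stay in the trial are tested less often than the protocol says. The visit 40 test comes too late to stop any dosing, so the rule in section 5.2 would rest on one scheduled test plus whatever a subject reports. What is at stake is exposure to study drug during an unrecognised pregnancy. Sample size, power and the primary analysis are not involved.

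**Working it through.** **Inputs.** Medication runs over study weeks 2 to 13, with three visits a week (section 6, Regular Evaluation Visits). The first visits of those weeks are 4, 7, 10 and so on to 37 (section 6.4). First dose is taken at visit 4. Doses come from Table 1 in section 5.2.

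**Calendar.** The first visit of study week w is visit 4 + 3(w − 2), so visit v falls (v − 4)/3 weeks after first dose.

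| Visit | Weeks after first dose |
|---|---|
| 16 | 12/3 = 4 |
| 19 | 15/3 = 5 |
| 28 | 24/3 = 8 |
| 40 | 36/3 = 12 |

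The listed schedule therefore leaves gaps of 5 weeks and then 12 − 5 = 7 weeks. The stated interval is 4 weeks. Counting from visit 1 does not help: screening lasts 1 to 4 weeks, so visit 1 to visit 19 spans 6 to 9 weeks. Counted from first dose, a four-weekly plan needs visits 16 and 28.

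**Mean delay.** Assume a pregnancy is equally likely to become detectable at any time in the 12 weeks. The mean dosing time before the next scheduled test is then the sum of squared gaps divided by (2 × 12).

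- As listed: (5² + 7²)/24 = 74/24 = 3.08 weeks.
- Visits 16 and 28: (4² + 4² + 4²)/24 = 48/24 = 2.00 weeks.

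**Planned dose after the last on-treatment test.** Week 2 is 3 × 0.5 + 4 × 1.0 = 5.5 mg. Weeks 3 to 12 are 70 × 2.0 = 140 mg. Week 13 is 7 × 1.0 = 7 mg. The total is 152.5 mg.

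- After visit 19: 42 × 2.0 + 7 = 91 mg, or 91/152.5 = 59.7%.
- After visit 28: 21 × 2.0 + 7 = 49 mg, or 49/152.5 = 32.1%.

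**Timing window.** Section 6.4 lets a non-weekly assessment slip by half the interval to its next collection. As listed, visit 19 could slip by 7/2 = 3.5 weeks, to 5 + 3.5 = 8.5 weeks after first dose. On a four-weekly schedule the slip is 4/2 = 2 weeks, giving a gap of up to 4 + 2 = 6 weeks. The window can move a test but cannot add one.

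**Women concerned.** The enrolment table in section 10.1.a plans 50. Section 5.3 expects under 30% of the sample, so fewer than 0.30 × 200 = 60. With equal allocation, about 25 would receive varenicline, or about 30 at the upper figure.

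**The case against.** The harm is conditional. A site that follows the narrative would test often enough, and the procedures flowchart (Attachment 3) is not in the text available, so it could not be checked. This is fair, but every visit list in the body gives the shorter schedule.

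Not every woman loses a test. Section 4.4.1 schedules an end-of-trial visit for those who stop early, and that visit includes a pregnancy test. A woman leaving before week 4 loses nothing, and one leaving between weeks 5 and 8 has one interim test either way. The loss falls on women who stay about 8 weeks or longer, or who leave between weeks 4 and 5. This stands, and it makes the count of extra tests an upper figure.

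The dose share assumes full titration, adherence and retention, and does not measure harm. That also stands: it describes the planned regimen only.

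The practical effect is small. Adverse events are asked about at every contact (section 8.2), a nurse or physician sees each subject weekly, and women of child-bearing potential must use contraception (section 4.2, item 12). The age range extends to 65, so fewer than 25 women on varenicline may be at risk. The modelled gain averages about 1.1 weeks per pregnancy. These points limit the size of the problem but do not resolve the contradiction.

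**Conclusion.** The inconsistency is real and lies in current text, within item 9 itself. If the visit lists govern, there is one scheduled test that can stop medication where a four-weekly plan needs two. The longest dosing time before a scheduled test is 7 weeks rather than 4, and the mean is 3.1 weeks rather than 2.0 under uniform onset.

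These figures assume that visits happen when planned. The window in section 6.4 permits longer gaps, so the 7 weeks is not a worst case. They also count from first dose and leave out a pregnancy that becomes detectable between the baseline test and first dose. The issue is a modest one of subject protection, and worth correcting because it is cheap to correct.

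**What to change.** In item 9 and section 6.4, replace visit 19 with visits 16 and 28 for the pregnancy test, and keep the baseline test and visit 40. Make the flowchart in Attachment 3 match. State that this test stays in its scheduled week and is exempt from the half-interval window. Trimming the narrative to fit the visit lists would also remove the contradiction, but by weakening a stated protection.

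The cost is a protocol amendment and one more test per woman who completes the trial (4 instead of 3): at most about 50 on the planned enrolment, and fewer than 60 under section 5.3. No extra visit or specimen is needed. Urine is collected at every visit (item 7), and the weekly drug screen already goes to the same laboratory at visits 16 and 28 (item 8).

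Because screening can last 1 to 4 weeks, a baseline test done at visit 1 would still be 5 to 8 weeks before visit 16. The change does not address that interval.

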6.1 Visit 1 (screening)

All screening procedures are to be completed prior to randomization (visits 1, 2, or 3). They may not necessarily be completed at the exact visit noted below.

Nurse or physician:

1. Informed consent and consent quiz
2. Medical history
3. Physical Exam (PE)
4. Vital signs weight (VITALS)
5. Electrocardiogram (EKG)
6. Concomitant medications (CONMEDS)
7. Adverse Events (AE)
8. CBC and blood chemistry including liver function tests (LFT) and CO2.
9. Urinalysis (UA)
10. Clinical Global Impression Scale, Observer (CGIO)
11. Supplemental questions
12. Clinical Institutes Withdrawal Scale for Alcohol Revised (CIWA AR)

Research staff

1. Breathalyzer (BAL)
2. CO
3. Cocaine Selective Severity Assessment (CSSA)
4. Treatment Services Review (TSR)
5. Minnesota Cocaine Craving Scale (MCCS)
6. Cocaine Craving Questionnaire (CCQ)
7. Fagerstrom Nicotine Tolerance Questionnaire (FNTQ)
8. Brief Substance Craving Scale (BSCS)
9. Multiple Choice Procedure (MCP)
10. Delay Discounting Questionnaire (DD)
11. Risk Assessment Battery (RAB)
12. Symptom Checklist-90-Revised (SCL-90-R)
13. Timeline Follow Back (TLFB)
14. Urine drug screen other than cocaine (UDS)
15. Urinary BE level (qualitative)
16. Cotinine
17. Clinical Global Impression Scale, Subject (CGIS)
18. Urine pregnancy test (UPT)(females)
19. Short Form Health Survey (SF-36)

